13 PROTOCOL VIOLATIONS

A protocol violation occurs when the patient or Sponsor/Investigator fails to adhere to significant protocol requirements affecting the inclusion, exclusion, patient safety and primary endpoint criteria. Protocol violations for this study include, but are not limited to, the following:

- Failure to meet inclusion/exclusion criteria
- Switching from component therapy to whole blood

Failure to comply with Good Clinical Practice (GCP) guidelines will also result in a protocol violation. The Sponsor/Investigator will determine if a protocol violation will result in withdrawal of a patient.

When a protocol violation occurs, it will be discussed with the Sponsor/Investigator and a Protocol Violation Form detailing the violation will be generated. This form will be signed by a Sponsor/Investigator or representative. A copy of the form will be filed in the site's regulatory binder and in the Sponsor/Investigator's files.

14 DATA SAFETY MONITORING

The UCLA Institutional Review Board has approved an Independent Medical Monitor, [name]. The Sponsor/Investigator and Independent Medical Monitor will review clinical data and probe for evidence of adverse events via discussion with the patient's clinical providers as described above. An interim analysis for safety is planned when approximately 50% of patients have been enrolled. The monitor will also ensure that records are maintained appropriately throughout the study.

15 STATISTICAL METHODS AND CONSIDERATIONS

Prior to the analysis of the final study data, a detailed Statistical Analysis Plan (SAP) will be written describing all analyses that will be performed. The SAP will contain any modifications to the analysis plan described in this protocol.

15.1 Data Sets Analyzed

All eligible patients who are enrolled in the study and receive at least one unit of blood, and who undergo TEG testing as described above, will be included in analysis.

Data sets include:

PI: [name]

1. Prospectively identified patients who received whole blood or component therapy and did not have severe TBI
2. Prospectively identified patients who received whole blood or component therapy and who had severe TBI (GCS 8 or less with evidence of brain injury on imaging)
3. Prospectively identified patients who received whole blood or component therapy, all patients regardless of TBI status
4. Prospectively identified male patients who received whole blood and who did not have severe TBI, compared to historical control male patients who received component therapy and who did not have severe TBI

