RATIONALE	Our study will test the feasibility of providing whole blood (WB) for resuscitation of adult male trauma patients in hemorrhagic shock and determine the effects of WB on clinical outcomes as well as the effects on coagulation, fibrinolysis, and inflammation, and hemolytic transfusion reactions compared to standard blood component therapy.
STUDY DESIGN	Prospective cohort study
PRIMARY OBJECTIVE	1. Compare volume of blood transfusion within 24 hours of admission between patients receiving whole blood and standard component therapy.
SECONDARY OBJECTIVES	The study will also compare: 1. Functional coagulopathy as measured by thromboelastography;

	
 2. 30-day mortality; 3. Number of units of blood products transfused by component/product; 4. Complications; 5. Hemolysis; 6. Wastage of blood units.
NUMBER OF PATIENTS	
Whole blood arm - 49 male patients over apparent age 18. Component therapy arm –49 male and female patients over apparent age 18.

PATIENT SELECTION CRITERIA	
Inclusion Criteria:
 
 • Whole blood arm: Male trauma patients over apparent age 18 with massive transfusion activation and presenting systolic blood pressure <100, who are receiving or will receive whole blood for initial resuscitation • Component therapy arm: Male and female trauma patients over apparent age 18 with massive transfusion activation and presenting systolic blood pressure <100, who have received, are receiving or will receive component therapy for initial resuscitation. 
Exclusion Criteria:
 
 • Patients with burns over >20% total body surface area
TEST PRODUCT, DOSE, AND ROUTE OF ADMINISTRATION	
Group O+ whole blood stored at 1-6 °C for up to 10 days. Patients may receive up to 4 units during the initial phase of the proposed study, to be increased to up to 6 units (see 5.2 Safety Evaluations) Product is administered to replace ongoing blood loss and restore/maintain hemodynamic stability and hemostasis. Product will be transfused intravenously as needed during initial traumatic resuscitation only. Following administration of whole blood if further transfusion is needed during initial trauma resuscitation, or after resuscitation is completed, the patient will receive standard

PI: [name]

	component therapy (packed red blood cells, plasma and platelets in a 1:1:1 ratio).

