5 CRITERIA FOR EVALUATION

5.1 Primary Efficacy Endpoint

The primary objective is to assess the clinical efficacy of whole blood compared to component therapy for trauma patients requiring massive transfusion. Primary analysis will compare volume of blood transfusion within 24 hours of admission for patients without severe TBI (defined as GCS \leq 8 and imaging evidence of brain injury) for patients who received WB versus component therapy for initial resuscitation.

Secondary Efficacy Endpoints

The secondary objectives will evaluate the effect on survival; the development of multiple complications related to survival; and wastage data. The full list of secondary endpoints is as follows:

1. Volume of blood transfusion within 24 hours of admission for patients with severe TBI (GCS \leq 8 and imaging evidence of brain injury) and for entire cohort of patients.
2. Thromboelastography parameters including maximum amplitude, reaction time, alpha angle, fibrinolysis, and platelet function at 3 and 6 hours of resuscitation, after every 6 units of whole blood equivalent (WB or PRBCs) given, at the time of completion of resuscitation (time of last unit of blood product given), and on ICU days 1, 3 and 5.
3. 30-day mortality;

PI: [name]

4. Duration of need for renal replacement therapy, mechanical ventilation, ICU admission, and hospital stay;
5. Number of units of blood products transfused by component/product during first 24 hours of admission and total hospitalization;
6. Complications which include clinical coagulopathy, infection, venous thromboembolism, cerebrovascular accident, acute coronary syndrome, transfusion-related lung injury, transfusion-associated cardiac overload during total hospitalization;
7. Hemolysis as measured by haptoglobin, bilirubin, lactate dehydrogenase, and direct antiglobulin on ICU day 1;
8. Wastage of blood units

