6.2 Inclusion Criteria

All trauma patients who present with SBP<100 who require activation of the massive transfusion protocol and who do not have severe burns (>20% total body surface area) will be eligible for enrollment. The study plans to include all such patients who present during the study period of approximately 2 years.

Within this group of patients, all adult male patients who received or will receive whole blood are eligible for inclusion in the whole blood group. All adult male patients who received or will receive component therapy initially are eligible for inclusion in the component therapy group. All adult female patients are eligible for inclusion in the component therapy group.

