9.1.6 Other Clinical Procedures

All patients will have, in addition to standard labs, additional labs drawn for thromboelastography, platelet function determination, and coagulation factor levels, on admission, after each 6 units of whole blood or PRBCs transfused, at 3 and 6 hours of resuscitation, at the time of hemostasis, and on ICU days 1,3 and 5. Tests for hemolysis will be performed along with regular clinical labs on ICU day 1. These labs will be drawn during clinical lab collection so no extra needle stick is required.

PI: [name]

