9.1.7 Adverse Events

Information regarding occurrence of adverse events will be captured throughout the study. Duration (start and stop dates and times), severity/grade, outcome, treatment and relation to study drug will be recorded on the case report form (CRF).

Morbidity and mortality in this study population (patients requiring massive transfusion for trauma) is high.²⁹ Therefore we expect a relatively large number of adverse events, and resulting SAE reports, for reasons unrelated to the study.

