15.3 Analysis of Primary Endpoint

Primary analysis compares volume of blood products transfused in the first 24 hours of admission in patients without severe TBI (severe TBI is defined as GCS \leq 8 and evidence of brain injury on imaging) receiving whole blood versus component therapy during initial resuscitation.

For continuous variables including the primary endpoint, the statistical method will depend on the distribution of the data. If the data appears to follow a normal distribution, a t-test will be used, otherwise, a nonparametric Wilcoxon rank sum test will be used.

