Current Medications	X				
Blood Chemistries	X	X			
Hematology/complete blood counts including serial platelet count monitoring	X	X			
TEG/platelet mapping and CAT testing	X			X	
Hemolysis testing			X		
Standard coagulation labs	X	X			
Fluid and blood product resuscitation volume	X				X
Vital Signs	X	X			
Inclusion/Exclusion Criteria	X				
Enrollment	X				
Concomitant Medications	X				X
Clinical outcomes					X
Discharge information					X

PI: [name]

Adverse Events	X	X			X
Operations/Procedures	X	X			X

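### Section 15.1 makes TEG testing a condition for entering any analysis, although the primary endpoint and seven of the eight secondary endpoints do not use TEG

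*Protocol*

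**What the plan says.** Section 15.1 (Data Sets Analyzed) is the only place where the protocol states in general terms who is analysed. Eligible, enrolled patients who "receive at least one unit of blood, and who undergo TEG testing as described above, will be included in analysis". Four data sets follow: prospective patients without severe TBI, those with severe TBI, all prospective patients, and male whole blood patients against male historical controls, both without severe TBI. None is exempted from the opening rule.

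The endpoints are defined without reference to TEG, apart from one. Section 15.3 states: "Primary analysis compares volume of blood products transfused in the first 24 hours of admission in patients without severe TBI". In the numbered list of Section 5.1, item 2 is the TEG endpoint: "Thromboelastography parameters including maximum amplitude, reaction time, alpha angle, fibrinolysis, and platelet function at 3 and 6 hours of resuscitation", with further time points up to ICU day 5. The other seven items are volume in severe TBI and in the whole cohort, 30-day mortality, durations of organ support and stay, units by product, clinical complications, hemolysis laboratory tests, and wastage.

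The schedule in Appendix I gives "Fluid and blood product resuscitation volume" its own row, separate from TEG. Section 9.1.6 plans TEG sampling for every patient "on admission, after each 6 units of whole blood or PRBCs transfused, at 3 and 6 hours of resuscitation", then at hemostasis and on ICU days 1, 3 and 5.

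**The concern.** A condition for entering an analysis should concern what that analysis needs. Here the condition is a study procedure carried out after arrival, and it governs analyses that make no use of its result. A patient whose transfused volume, survival, complications and unit counts are all known would be dropped from each of those comparisons for want of a TEG sample.

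The loss need not be random. Section 17.3 describes the TEG draw as study-related testing that begins in emergency resuscitation, before patients can be informed. Section 9.1.7 says "Morbidity and mortality in this study population (patients requiring massive transfusion for trauma) is high". Enrolment may also follow treatment: the Synopsis admits component therapy patients "who have received, are receiving or will receive component therapy for initial resuscitation", and Section 6.2 says "all adult male patients who received or will receive whole blood are eligible for inclusion in the whole blood group". A patient who dies very early, or who is identified late, is the one most likely to have no sample. Such patients may also have unusual transfusion volumes, and early deaths bear directly on the mortality endpoint.

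Treatment is not randomised (Section 8.1) and the study is not blinded (Section 8.2). Selection on a post-arrival event therefore adds a source of bias to a comparison that already relies on adjustment for confounding.

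**Working it through.** **1. Which endpoints need TEG.** Primary endpoint: no. Secondary endpoints in Section 5.1: item 2 yes; items 1, 3, 4, 5, 6, 7 and 8 no. Coagulopathy in item 6 is clinical and is not tied to TEG. So 8 − 1 = 7 of the eight secondary endpoints do not need it.

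**2. The protocol's own sample size.** The sample size text under Section 15.5 plans 49 per arm and expects about 18 with severe TBI:
- 49 − 18 = 31 per arm, as stated.
- 18/49 = 36.7%, inside the stated 35–40%.
- At the limits of that range, 49 × 0.65 = 31.9 and 49 × 0.60 = 29.4.

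Severe TBI is the only loss allowed for. Nothing is set aside for missing TEG.

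**3. Implied effect.** The protocol gives neither an effect size nor an SD in figures, so the 80% power cannot be reproduced directly. Working backwards with a two-sample t-test, type I error 0.05 (two-sided assumed), 31 per arm and 80% power gives a standardised difference d = 0.723.

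**4. Random loss from both arms.** One patient is 1/31 = 3.2% of an arm's primary set. With d held at 0.723:

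| Lost per arm | n per arm | Power |
|---|---|---|
| 0 | 31 | 80.0% |
| 1 | 30 | 78.7% |
| 2 | 29 | 77.2% |
| 3 | 28 | 75.7% |

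For the Wilcoxon test, approximated by an efficiency of 3/π with d re-solved to 0.741, power agrees with the table to within 0.1 percentage point.

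**5. Selective loss from one arm.** Suppose k of an arm's 31 patients are lost and their mean volume differs from that of the remaining patients by 1 SD (assumed). The full-arm mean equals the remaining mean plus (k/31) × 1 SD, so dropping them shifts the between-group difference by k/31 SD:

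| k | Shift (SD) | Share of d = 0.723 |
|---|---|---|
| 1 | 1/31 = 0.032 | 4.5% |
| 2 | 2/31 = 0.065 | 8.9% |
| 3 | 3/31 = 0.097 | 13.4% |

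The sign depends on which arm loses patients and on whether their volumes are above or below the rest.

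**6. Fit with other sections.** The sample size text also promises a secondary comparison of the whole enrolled cohort, with and without TBI, and states no TEG condition. That does not agree with the rule in Section 15.1. The historical controls of data set 4 were treated in the five years before the study (Section 6.1), so they were neither enrolled nor tested under the study schedule. The lead-in does not fit them.

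**The case against.** The strongest reply is that almost nobody would be lost. TEG is planned for every patient, starting at admission, and Section 9.1.6 says the samples are taken with the clinical laboratory draw, so no extra needle stick is needed. If one sample is enough, a patient fails the rule only by missing every time point, and a patient identified late can still be sampled up to ICU day 5. This stands, and it is why the expected loss is small. It depends, however, on reading the rule as at least one sample. Section 15.1 refers back to the testing described earlier without saying so. If the full schedule were required, patients who died or left the ICU before day 5 would drop out of the primary and mortality analyses.

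A second reply is that the sentence says who will be included, not who is excluded, and that the data sets, Section 15.3 and the sample size text describe their populations without TEG. Grammatically that is fair. But as the only general definition under its heading, the sentence works as a requirement; otherwise naming TEG would serve no purpose.

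Third, Section 15 allows a later SAP to modify the plan. That lowers the consequence but does not correct the rule as it stands.

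Fourth, the magnitudes rest on assumed losses, and the protocol states no mechanism that would confine loss to one arm. A loss of one or two per arm is also close to the protocol's own tolerance of 29.4 to 31.9. All of this is correct: the figures give a scale, not a forecast.

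Finally, the historical controls already have selection criteria in Section 6.1, so that point is one of wording and does not block the analysis.

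**Conclusion.** The concern holds. Section 15.1 states a rule that, followed as written, removes patients from the primary analysis and from seven of the eight secondary analyses for lack of a test those analyses do not use. This should be fixed, although a large effect is unlikely.

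The size and direction of any bias cannot be derived from the protocol. On the illustrative scale, random loss of 1 to 3 patients per arm takes power from 80% to between 79% and 76%. Selective loss of the same number from one arm moves the group difference by 0.03 to 0.10 SD, which is 4.5% to 13.4% of the implied effect. These figures assume that the stated 80% power is right, that the test is two-sided and, for the selective case, a 1 SD difference in volume. Confidence is high about the wording and its unsuitability, and much lower about how many patients it would affect.

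**What to change.** Amend Section 15.1 in three respects.

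- For the primary endpoint and every secondary endpoint except the TEG item, analyse all eligible, enrolled patients who received at least one unit of blood, with no TEG condition.
- Apply a TEG condition to the TEG endpoint only, and say what satisfies it, for example at least one evaluable sample.
- State that the historical controls in data set 4 are selected by the Section 6.1 criteria, without severe TBI and with at least one unit received, and that no enrolment or TEG condition applies to them.

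The cost is two or three sentences. No new data are needed and no study procedure changes.

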STATISTICS Primary Analysis Plan	For continuous variables including the primary endpoint (volume of blood products transfused during the first 24 hours of admission), the statistical method will depend on the distribution of the data. If the data appears to follow a normal distribution, a t-test will be used, otherwise, a nonparametric Wilcoxon rank sum test will be used. To analyze coagulopathy over time a mixed effects linear regression model will be used. A mixed effects linear regression model will also be used to adjust for confounding variables such as sex, age, comorbidities, severity of injury, and physiologic parameters of shock including pH and temperature, and use of a rapid transfuser (which more effectively warms blood).
Rationale for Number of Patients	A sample size of 49 whole blood group (study drug) and 49 component therapy group (control) patients (98 patients total) is estimated. 18 of these per group are expected to have severe TBI and will be excluded from primary analysis, leaving 31 patients per group for the primary analysis. Using a Type I error rate of 0.05, and effect size based on reduction of PRBC and plasma transfusions described in the sensitivity analysis in a study by Cotton et al, 31 patients per group is expected to have 80% power to detect a significant difference in volume of transfusion in 24 hours. ¹

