4 STUDY DESIGN

4.1 Study Overview

This is a single center, prospective cohort study. Enrollment of approximately 98 patients is planned, 49 receiving whole blood and 49 receiving component therapy. This is an observational study planned during initiation of a change in practice at our institution initially allowing up to 4 units of whole blood transfusion for adult male trauma patients. If initial patients receiving whole blood show no evidence of hemolysis and thrombocytopenia compared to patients receiving component therapy, up to 6 units of whole blood transfusion will be allowed (see below, and section 5.2, Safety Evaluations). Patients in the whole blood, or index, group are adult male trauma patients presenting in hemorrhagic shock (systolic blood pressure < 100) requiring massive transfusion activation who receive whole blood for resuscitation. Two control groups will be utilized. The prospective control group consists of adult male patients who present during times when whole blood is not available, as well as adult female patients, presenting in hemorrhagic shock (systolic blood pressure <100) requiring massive transfusion activation. Additionally, a second control group consisting of historical

PI: [name]

controls receiving component therapy will be analyzed (see Section 6, Patient Selection, for details of index and control groups).

All patients will have, in addition to standard labs, additional labs drawn for thromboelastography, platelet function determination, and coagulation factor levels (see Section 9.1.6, Other Clinical Procedures, for details of specific lab tests and timing).

Patients who meet all inclusion criteria and none of the exclusion criteria will be enrolled into the study.

Total duration of patient participation will be approximately 1 year (365 days), or the duration of the hospital stay, whichever is shorter. This includes up to 5 days of laboratory testing during initial resuscitation and subsequent admission, and up to one year of follow up via chart review if the patient remains in the hospital. Total duration of the study including recruitment and follow up is expected to be 2 years.

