6 PATIENT SELECTION

6.1 Study Population

All trauma patients who present with SBP<100 who require activation of the massive transfusion protocol and who do not have severe burns (>20% total body surface area) will be eligible for enrollment.

Enrollment of male and female patients:

PI: [name]

At UCLA and at least two other institutions²⁸ the standard of care for traumatic resuscitation for adult males is either:

- 1) Low anti-A anti-B titer (<1:100) group O+ whole blood
or, when whole blood is not available,
- 2) Component therapy, consisting of group O+ PRBCs, group AB or A plasma, and untyped platelets

The standard of care for adult females is component therapy, consisting of group O- PRBCs, group AB or A plasma, and untyped platelets. Group O- whole blood is not available at our institution at this time. During a critical traumatic resuscitation, it is often impossible to determine precise age and menopausal status before initiation of transfusion. In order to avoid any possibility of alloimmunization of reproductive-age females, the UCLA Blood and Blood Derivatives Committee has approved group O+ whole blood only for use in males.

The index and control groups in the study therefore consist of:

- 1) Index group: male trauma patients presenting with SBP<100 who require activation of the massive transfusion protocol and who do not have severe burns >20% TBSA who receive whole blood;
- 2) Prospective control group: Prospectively-identified cohort of patients who present during the study with SBP<100 who require activation of the massive transfusion protocol and who do not have severe burns >20% TBSA but who are either not eligible or not able to receive whole blood. This category consists of patients who are female (who are not eligible to receive whole blood) and male patients who present when whole blood is out of stock;
- 3) Historical control group: male trauma patients who presented with SBP<100 who required activation of the massive transfusion protocol and who did not have severe burns >20% TBSA who received component therapy for traumatic hemorrhage requiring massive transfusion protocol activation, during the 5 years prior to initiation of the study.

A mixed effects linear regression model will be used to adjust for confounding variables, including sex.

Enrollment of patients of unknown precise age:

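### The only men-only data set in Section 15.1 uses pre-study controls, so calendar change in transfusion volume cannot be told apart there from a whole blood effect

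*Protocol*

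**What the plan says.** Section 4.1 of the protocol states: "Two control groups will be utilized". The prospective group consists of women, plus men who arrive when whole blood is out of stock. The historical group (Section 6.1) consists of men given component therapy "during the 5 years prior to initiation of the study".

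Section 15.1 lists four data sets. Data sets 1 to 3 are prospective: without severe TBI, with severe TBI, and all patients. Data set 4 is "Prospectively identified male patients who received whole blood and who did not have severe TBI, compared to historical control male patients", again without severe TBI.

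Section 15.3 defines the primary analysis, in patients without severe TBI, as a comparison of those "receiving whole blood versus component therapy during initial resuscitation", without naming a control group. The test is an unadjusted t-test or Wilcoxon rank sum test. The synopsis, Section 6.1 and Section 15.4 also plan a mixed effects regression that adjusts for confounders including sex. Calendar period is not among the confounders named, although the list is open.

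Sections 6.2 and 8.1 confirm that men given components during the study are enrolled. Section 15.1 lists no data set that sets them against whole blood men alone, or against the historical men.

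**The concern.** Every whole blood patient is male, while the concurrent control arm is "49 male and female patients over apparent age 18" (synopsis). A reader who wants a like-sex result from the listed data sets is therefore sent to data set 4. There, every control precedes study start and every whole blood patient follows it. Any change over those years in transfusion practice, bleeding control or case mix moves the estimate exactly as a treatment effect would. A downward trend in volume would look like benefit; an upward trend would hide it.

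The study enrols the group that could expose this. Concurrent and historical component men received the same kind of treatment in different periods, so a difference between them signals drift or a change in case mix. Section 15.1 does not list that comparison.

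**Working it through.** **The plan's own figures.**
- The synopsis says "18 of these per group are expected to have severe TBI and will be excluded from primary analysis". From 49 per group, 49 − 18 = 31, which reproduces.
- It then says "31 patients per group is expected to have 80% power to detect a significant difference in volume of transfusion in 24 hours". This cannot be reproduced, because the protocol gives no effect size or SD. At a two-sided 0.05, 31 per group with 80% power implies a standardized difference of (1.960 + 0.842) × √(2/31) = 0.71 SD.

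**Which data set is primary.** The wording of Section 15.3 alone fits data sets 1 and 4. The 31 per group, however, come from 49 + 49 enrolled patients with men and women in the component arm. The historical group is male only and lies outside that sample. Data set 1 is therefore primary by implication.

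**Calendar gap in data set 4.** The inputs are a 5-year historical window (Section 6.1) and a 2-year study (Section 4.1). I assume uniform accrual over both.
- Mean gap: 5/2 + 2/2 = 3.5 years.
- Largest gap: nearly 5 + 2 = 7 years.

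**Illustration of drift.** Assumed, not in the protocol: a yearly fall of 3% or 5% in 24-hour volume, lognormal volume with CV 1.0, 31 whole blood men, 100 historical men and no whole blood effect.
- Log-scale SD: √ln(1 + 1²) = 0.83.
- SE: 0.83 × √(1/31 + 1/100) = 0.171.
- At 3%: apparent reduction 1 − 0.97^3.5 = 10%; log shift 0.107; 0.107/0.171 = 0.62 SE; two-sided rejection 0.091 + 0.005 = 0.096, about 10%.
- At 5%: apparent reduction 1 − 0.95^3.5 = 16%; log shift 0.180; 0.180/0.171 = 1.05 SE; two-sided rejection 0.181 + 0.001 = 0.18.

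A simulation in SD units, with 31 to 150 historical men, gave 11–14% rejections at a drift of 0.05 SD a year and 27–42% at 0.10. A drift of 0.71/3.5 = 0.20 SD a year would reproduce the whole effect for which the study is powered.

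**What a concurrent men-only contrast could deliver.** The male share of the 31 controls is not given. If it is 30%, 50%, 70% or 80%, there are 9, 16, 22 or 25 component men. Power at 0.71 SD against 31 whole blood men is then about 47%, 64%, 72% or 75%.

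**What the drift check could deliver.** Compare m concurrent with 100 historical component men, keeping the log SD of 0.83. The 95% interval extends from the estimated ratio by a factor of exp(1.96 × 0.83 × √(1/m + 1/100)). This is about 1.76 for m = 9, 1.55 for m = 16 and 1.44 for m = 25. The illustrated drifts are factors of 1/0.899 = 1.11 and 1/0.836 = 1.20. The check can therefore reveal a large drift but cannot rule out a modest one.

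**Whether a year-of-admission term helps.** The two periods do not overlap, so the term can only extrapolate a trend. Under uniform accrual the within-group sum of squares of calendar time is n × 25/12 + 31 × 4/12, and the added variance (in units of σ²) is 3.5² divided by that sum.
- n = 100: 12.25/218.7 = 0.056 is added to 1/31 + 1/100 = 0.042. The SE grows by √(0.098/0.042) = 1.5.
- n = 31: 12.25/74.9 = 0.164 is added to 2/31 = 0.065. The SE grows by √(0.228/0.065) = 1.9.

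**The case against.** Four points can be made in the plan's defence.

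**The primary control group can be identified.** A reader might infer from Section 15.3 that data sets 1 and 4 both count as primary, so that the endpoint is tested twice at 0.05 and the type I error rises to 8.5–9.1%. The documents do not support that. The enrolled 49 + 49, the mixed-sex component arm and the 31 per group all point to data set 1. Section 15.1 also limits analysis to enrolled patients with the study's TEG testing, which pre-study controls would not generally meet. This objection stands in full.

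**The planned sex adjustment already uses the concurrent men.** No woman receives whole blood. In a model with whole blood and sex as main effects, the sex term absorbs the women's mean, and the whole blood coefficient equals whole blood men minus concurrent component men. With further covariates the women inform only slopes and residual variance. This largely stands: data set 4 is the only men-only set listed, but not the only like-sex information planned. The stated primary test is nevertheless unadjusted, and the adjustment does nothing for drift in data set 4.

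**Much of this may belong in the SAP.** The covariate list is open, so calendar period is not excluded. A reader might infer that the plan throws the concurrent men away; it keeps them and merely omits the comparison. That is fair. But the protocol itself fixes the data sets, and the one it fixes for men is the confounded one.

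**The size rests on assumed inputs.** The protocol documents no trend in component practice. That is correct, and the percentages illustrate data set 4 only.

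**Conclusion.** The point holds as a modest improvement. Data set 4 cannot separate a whole blood effect from calendar change. With a mean gap of about 3.5 years, a fall of 3% or 5% a year would produce an apparent 10% or 16% reduction and about 10% or 18% rejections with no whole blood effect. Those figures depend on the assumed drift, CV 1.0, 100 historical men and uniform accrual. The structural confounding depends on none of them.

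Nothing here shows that the primary result is biased by calendar time or that its type I error is inflated. Data set 1 uses concurrent controls.

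**What to change.** 1. In Section 15.1, label data set 4 as supportive.
2. Add a contrast of whole blood men with concurrent component men, both without severe TBI. Report it as an estimate with a confidence interval rather than a test, since its power is likely to be below 80%. Note that it is close to the whole blood coefficient of the planned sex-adjusted model.
3. Compare concurrent with historical component men without severe TBI, and print the result beside data set 4 as a drift and case-mix check. Do not interpret data set 4 as a whole blood effect without it, and do not read a non-significant difference as proof of no drift.
4. As clarification only, state in Section 15.3 that the primary comparison is data set 1.
5. Do not rely on a year-of-admission term in data set 4, because it would rest on trend extrapolation.

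The cost is a few sentences and two tables from data the study already plans to collect. Both tables will be imprecise if few concurrent component men are enrolled.
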